# 9.7.2 Sample Size Determination

The FOPal registry study aims to enrol a minimum of 67 participants with FOP treated with palovarotene and 33 participants with FOP not treated with palovarotene. Approximately half of the participants in each cohort (exposed and unexposed) will be paediatric (8 years to less than 18 years of age for girls and 10 years to less than 18 years of age for boys).

# 9.7.3 Statistical and Analytical Methods

This section is a summary of the planned statistical analysis of the primary and secondary endpoints for the FOPal registry study. A Statistical Analysis Plan (SAP) with a more technical

PAGE 61 OF 287

and detailed description of the statistical analysis, with a table, a figure and listing templates, will be developed as a separate document.

#### 9.7.3.1 Statistical Analyses – General Considerations

The statistical analyses will be performed by an external SP, managed by the sponsor's Medical Affairs Biometry Department.

Statistical evaluation will be performed using Statistical Analysis System (SAS)® (Version 9.2 or higher).

No formal statistical testing will be performed and all the analyses will be primarily descriptive in nature. When appropriate and unless otherwise specified, 2-sided 95% CI will be displayed and if p-values are presented, they will be for exploratory purposes only.

Descriptive summary statistics will include the number of documented data, number of missing data and the following:

- Mean, standard deviation, 95% CI of the mean/median when appropriate, median, minimum and maximum for continuous variables;
- Frequency count and percentages for categorical nominal variables.

Missing data will not be replaced but will be summarised in all relevant tables.

Percentages will be based on the number of non-missing observations.

#### 9.7.3.2 Analysis of Primary Endpoints – Safety Evaluation

Adverse Events, Special Situations and Adverse Events of Special Interest

All AEs, Special Situations and AESIs will be included in the participant data listings using the Safety Exposed Population. Analyses and summary tables will be presented in the Safety Exposed Population.

Adverse events will be coded according to MedDRA and will be classified by PT and SOC. Adverse events listings will be presented by participant, SOC and PT.

The incidence of all reported TEAEs, serious and nonserious treatment-related TEAEs, all serious TEAEs, all nonserious TEAEs, AEs leading to death, AEs leading to treatment discontinuation, Special Situations and AESIs will be tabulated separately. In addition, summary tables for TEAEs will be presented by maximum intensity and drug relationship (investigator-reported causality assessment).

A TEAE is defined as any AE that occurs from the first dose of marketed palovarotene intake until the last palovarotene intake + 30 days if:

- It was not present prior to receiving the first dose of palovarotene; or
- It was present prior to receiving the first dose of palovarotene but the event worsened during treatment with palovarotene.

All TEAEs will be flagged in the AE listings.

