# 9.2.4 Registry Study Duration

The duration of the FOPal registry study is up to 11 years, with an enrolment period of maximum 10 years from first participant, first visit, and a minimum of 1 year of data collected for participants who are enrolled within that period.

Participant enrolment will start on the date that palovarotene is commercially available in any given country for exposed participants, and once the investigational site has been activated for all participants.

The investigator must ensure that the participant receives appropriate medical follow-up and this should be properly documented in the participant's medical records and eCRFs regarding:

- AEs or their sequelae (any AE, based on the investigator's opinion, not only those assessed as related) that persist after the date of palovarotene discontinuation for exposed participants.
- Medical events of special interest (growth outcomes, including PPC, and fractures) for unexposed participants for the entire study duration.

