## 9.3 Endpoints and Variables

## 9.3.1 Endpoints

# 9.3.1.1 Primary Endpoints

- Incidence and description of all TEAEs, whether or not they are considered as related to palovarotene;
- Incidence and description of all serious TEAEs, whether or not they are considered as related to palovarotene;
- Incidence and description of all nonserious TEAEs whether or not they are considered as related to palovarotene;
- Incidence and description of all serious and nonserious treatment-related TEAEs.

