# 9.3.1.2 Secondary Endpoints

For participants with FOP exposed and unexposed to palovarotene:

- Raw values and change from Baseline in CAJIS total score at each Follow-up Visit;
- Raw values and shift from Baseline in use of assistive devices and adaptations for daily living at each Follow-up Visit;
- Raw values and change from Baseline in % of worst score for total score, upper extremities subscore and mobility subscore using age-appropriate forms of the FOP-PFQ at each Follow-up Visit;
- Raw values and change from Baseline in observed and % predicted FVC at each Follow-up Visit;
- Raw values and change from Baseline in observed and % predicted FEV1 at each Follow-up Visit;
- Raw values and change from Baseline in absolute and % predicted FEV1/FVC ratio at each Follow-up Visit;

PAGE 51 OF 287

- Raw values and change from Baseline in observed and % predicted DLCO at each Follow-up Visit;
- Raw values and change from Baseline in physical and mental function (mean global physical and mental health score converted into T-scores) for participants ≥15 years old and overall QoL (mean total score converted into T-scores) for participants <15 years old using age-appropriate forms of PROMIS Global Health Scale at each Follow-up Visit;
- Annualised frequency of flare-ups, categorised by overall occurrence;
- Number of locations impacted by movement mobility change per participant annually and change from Baseline;
- Any movement mobility change (better movement/the same movement/slightly worse movement/moderately worse movement/severely worse movement) by body location and annually;
- Evolution of locations impacted by movement mobility change (how many times a location is impacted) per body location, annually and change from baseline;
- Movement mobility outcomes (change in extra bone growth and change in movement), causes, associated symptoms if preceded by a flare-up event by body location;
- Frequency, severity, outcome and descriptive characteristics of any fractures, overall and at each Follow-up Visit, categorised by location;
- Annualised frequency and descriptive characteristics of bone fractures, categorised by overall occurrence and location;
- Incidence of pregnancy.

For participants with FOP exposed to palovarotene who become pregnant while enrolled in FOPal:

- Pregnancy characteristics and outcomes;
- Pregnancy-related AEs through the first year postpartum;

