1.1 Does the protocol specify timelines for				
1.1.1 Start of data collection 	$\boxtimes$			6
1.1.2 End of data collection 				6
1.1.3 Progress report(s)				N/A
1.1.4 Interim report(s)		$\boxtimes$		6
1.1.5 Registration in the EU PAS Register				6
1.1.6 Final report of study results.				6
Comments:				

Section 2: Research question	Yes	No	N/A	Section Number
2.1 Does the formulation of the research question and objectives clearly explain:				
2.1.1 Why the study is conducted? (e.g. to address an important public health concern, a risk identified in the risk management plan, an emerging safety issue)				7.4, 8.1
2.1.2 The objective(s) of the study?	$\boxtimes$			8.2
2.1.3 The target population? (i.e. population or subgroup to whom the study results are intended to be generalised)	$\boxtimes$			9.2.3
2.1.4 Which hypothesis(-es) is (are) to be tested?			$\boxtimes$	N/A
2.1.5 If applicable, that there is no a priori hypothesis?				N/A

Comments: Analyses in this study are primarily descriptive in nature, no formal statistical testing will be performed, therefore hypotheses are not applicable.

 Date from which information on the first study is first recorded in the study dataset or, in the case of secondary use of data, the date from which data extraction starts.

 Date from which the analytical dataset is completely available.

PAGE 97 OF 287

Section 3: Study design	Yes	No	N/A	Section Number
3.1 Is the study design described? (e.g. cohort, case-control, cross-sectional, other design)	$\boxtimes$			9.1
3.2 Does the protocol specify whether the study is based on primary, secondary or combined data collection?	$\boxtimes$			9.4
3.3 Does the protocol specify measures of occurrence? (e.g. rate, risk, prevalence)			$\boxtimes$	N/A
3.4 Does the protocol specify measure(s) of association? (e.g. risk, odds ratio, excess risk, rate ratio, hazard ratio, risk/rate difference, number needed to harm (NNH))				N/A
3.5 Does the protocol describe the approach for the collection and reporting of adverse events/adverse reactions? (e.g. adverse events that will not be collected in case of primary data collection)	$\boxtimes$			11
Comments: Analyses in this study are primarily descript testing will be performed.	ive in r	nature, 1	no forn	nal statistical
			1	1 ~
Section 4: Source and study populations	Yes	No	N/A	Section Number
4.1 Is the source population described?	$\boxtimes$			9.2.3

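### The primary TEAE and AESI incidence has no time base although exposure differs widely between participants; exposure-adjusted rates and cumulative incidence should stand beside the percentages

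*Protocol*

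**What the plan says.** **Endpoint.** Protocol 9.3.1.1 lists "Incidence and description of all TEAEs, whether or not they are considered as related to palovarotene" as the first primary endpoint. Parallel entries cover serious, nonserious and treatment-related TEAEs. None has a denominator or a unit of time.

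**Analysis.** Section 9.7.3.2 says that "The incidence of all reported TEAEs, serious and nonserious treatment-related TEAEs, all serious TEAEs, all nonserious TEAEs, AEs leading to death", together with AEs leading to treatment discontinuation, Special Situations and AESIs, will be tabulated in the Safety Exposed Population. The general rules in 9.7.3.1 are "Frequency count and percentages for categorical nominal variables" and "Percentages will be based on the number of non-missing observations".

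**Risk window.** A TEAE is counted from the first marketed dose "until the last palovarotene intake + 30 days if" it was new or had worsened on treatment.

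**Follow-up.** Section 9.2.4 states: "The duration of the FOPal registry study is up to 11 years, with an enrolment period of maximum 10 years from first participant, first visit". It adds a minimum of 1 year of data per participant. Under 9.2.8, exposed participants who no longer receive palovarotene are withdrawn, except after a safety concern or pregnancy. Section 9.2.9 follows those who discontinue for up to 30 days.

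**Contrast.** A time base is given elsewhere. The secondary endpoints include annualised flare-up frequency and "Annualised frequency and descriptive characteristics of bone fractures, categorised by overall occurrence and location". In the ENCePP checklist (Appendix 1), the item "3.3 Does the protocol specify measures of occurrence? (e.g. rate, risk, prevalence") is marked not applicable.

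**The concern.** Incidence can mean a proportion of participants, a rate per person-year, or a cumulative risk by a given time. When everyone is observed for the same time, the choice matters little. Here it matters, because one exposed participant may contribute a few weeks on drug and another many years.

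A proportion over such unequal windows rises with follow-up even when the underlying rate is unchanged. The protocol plans summaries by age group and gender (9.7.4) and interim reports (9.7.5). Readers will also set the results beside the clinical studies, where mean exposure was 94.1 weeks (7.3.1). Each of these comparisons may set groups with different follow-up side by side, and a difference in percentages could then come from follow-up alone.

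AESIs with delayed onset are the sharpest case. Section 7.3.1 reports that PPC on chronic-only dosing typically appeared between 12 and 18 months. Participants who leave before then would count fully in the denominator with little opportunity to have the event.

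**Working it through.** **1. The plan's own duration.** Maximum enrolment of 10 years plus the 1-year minimum gives 10 + 1 = 11 years. The milestones agree: Q4 2024 to Q4 2035 is 11 years.

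**2. Range of the TEAE window.** The shortest case is one dose plus 30 days, about 31 days. The longest prospective case is about 11 years. Both are extremes. The withdrawal rule means that the 1-year minimum does not bind early discontinuers. Non-naïve participants can exceed 11 years, because their window opens at the first marketed dose, before consent.

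**3. One rate, different follow-up.** With a constant rate *r* per year, the proportion with at least one event by time *t* is 1 − exp(−*r t*). The documents give no event rate for this registry, so *r* is varied. The value 0.225 is an illustration from 7.3.1: 13 of 39 participants aged ≥8/10 to <14 years had PPC, and 94.1/52.18 = 1.803 years, so −ln(1 − 13/39)/1.803 = 0.225. It assumes that the overall mean exposure applies to that subgroup.

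| Assumed rate per year | 31 days | 1 year | 2 years | 5 years | 11 years |
|---|---|---|---|---|---|
| 0.05 | 0.4% | 4.9% | 9.5% | 22.1% | 42.3% |
| 0.10 | 0.8% | 9.5% | 18.1% | 39.3% | 66.7% |
| 0.225 | 1.9% | 20.1% | 36.2% | 67.5% | 91.6% |
| 1.0 | 8.1% | 63.2% | 86.5% | 99.3% | 100.0% |

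**4. A whole cohort.** Inputs: 67 exposed participants (9.5), entry spread evenly over 10 years, cut-off at year 11, and assumed discontinuation at *d* per year. Participant *i* has potential follow-up aᵢ between 1 and 11 years. The 30-day tail is ignored.

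- Expected proportion with an event: mean of [*r*/(*r*+*d*)] × [1 − exp(−(*r*+*d*)aᵢ)]
- Expected person-years at risk: sum of [1 − exp(−(*r*+*d*)aᵢ)]/(*r*+*d*)

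For *r* = 0.10:

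| Discontinuation per year | Crude percentage | Person-years at risk | First events per 100 person-years |
|---|---|---|---|
| 0 | 42.8% | 287 | 10.0 |
| 0.2 | 25.5% | 171 | 10.0 |
| 0.5 | 15.1% | 101 | 10.0 |

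The rate column is the expected events over the person-years; in the first row, 0.428 × 67 = 28.7 events and 28.7/287 = 0.100. The crude percentages for the same three discontinuation rates are 25.1%, 14.3% and 8.1% at *r* = 0.05, and 64.6%, 41.8% and 26.5% at *r* = 0.20.

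**5. Where person-time may start.** Section 9.7.3.4 sets the index date for non-naïve participants at the first marketed dose. Note n to Table 3 starts AE, SAE and AESI collection at signed consent. Section 9.3.2.5 captures earlier events only as retrospective important medical events related to the disease. Counting person-years from index would add time in which most TEAEs are not recorded, and would bias the rate downward.

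**The case against.** The strongest reply is that this belongs to the SAP. Section 9.7.3 calls itself a summary and leaves technical detail and table templates to a separate SAP, which is not at hand. Exposure-adjusted columns are often decided there, and nothing in 9.7.3.2 rules them out. A reader might infer that the protocol commits the primary endpoint to a percentage of participants. It does not say so: 9.7.3.2 says only that incidence is tabulated, and the percentage reading comes from the general rule in 9.7.3.1. That part of the reply stands. It does not remove the point, because the protocol states annualised measures for flare-ups and bone fractures and leaves its primary measure undefined. Fractures show the inconsistency: 9.7.3.4 tabulates them as plain incidence, while 9.3.1.2 annualises them.

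Two further replies have weight. First, the primary analysis describes one cohort without testing, treatment duration is reported (9.7.3.5), and the exposed-versus-unexposed outcomes are annualised or use height z-scores. However, duration is not tied to TEAE incidence, and the subgroup and interim summaries still invite comparison. Second, the checklist is weak evidence. It also marks selection bias not applicable although 9.7.3.4 uses propensity-score weighting to reduce it. Its entry on occurrence cannot show an intention to avoid rates.

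**Conclusion.** The point holds as a recommended improvement to the stated method. The primary incidence has no time base, the only stated rule for categorical data is counts and percentages, and exposure is unequal by design. Followed as written, the summaries would mix risk with length of follow-up. At an assumed 0.10 per year, groups with identical risk followed for 2 and 5 years would show about 18% and 39%. In the cohort illustration, the same rate appears as anything from 15.1% to 42.8%, depending on discontinuation.

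A reader might go further and infer that the percentages would reflect follow-up instead of risk. The documents do not support that: a crude percentage carries both, and frequent early events are less affected in the later years (at 1.0 per year, 86.5% at 2 years against 99.3% at 5). Nor should a range of one month to 11 years be read as typical. All event and discontinuation rates here are assumptions, apart from the PPC-based illustration, which rests on a constant hazard and a borrowed mean exposure. This is a question of summary statistics and touches no clinical rule.

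**What to change.** In 9.3.1.1 and 9.7.3.2, keep the crude count and percentage and add:

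- **Rates.** Participants with a first event per 100 person-years at risk, with exact Poisson 95% CIs, and event rates for recurrent events. Give both overall and by the planned age and gender subgroups.
- **Cumulative incidence at fixed times**, for example 1, 2 and 5 years, for serious TEAEs and each AESI, because the hazard may not be constant.
- **Person-time for first-event rates.** Start at the later of first marketed dose and signed consent. End at first event or last intake + 30 days, or at end of observation if that comes sooner.
- **Time scale for cumulative incidence.** Keep first marketed dose as time zero and enter non-naïve participants late, at consent.
- **Pre-consent experience.** Show the pre-consent time and retrospective events of non-naïve participants separately.

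Bring ENCePP item 3.3 into line with the measure chosen. If the SAP already defines these measures, a cross-reference and one defining sentence in the protocol would suffice.

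The cost is wording, some programming and extra table columns. Treatment dates (9.3.2.9) and event dates (9.3.2.5) are already collected. A single rate assumes a roughly constant hazard; the cumulative incidence offsets that weakness.

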# 9.7.3.3 Analysis of Secondary Endpoints – Effectiveness Evaluation

Effectiveness data will be included in the participant data listings using the Safety Exposed and the Safety Unexposed Populations. Analyses and summary tables will be presented in the Safety Exposed and the Safety Unexposed Populations.

Data will be tabulated descriptively, i.e. the number and percentage of participants for each category for categorical parameters and the number, mean, standard deviation, 95% CIs of the mean/median when appropriate, median, minimum and maximum for continuous parameters will be tabulated.

**PAGE 62 OF 287** 

Cumulative Analogue Joint Involvement Scale

Actual values as well as the change from the Baseline Visit in CAJIS total score will be presented for each visit.

Actual values as well as the shift from the Baseline Visit in ambulation and use of assistive devices/adaptations for daily living will also be presented for each visit.

Use of Assistive Devices and Adaptations for Daily Living

Actual values as well as the shift from the Baseline Visit in the use of assistive devices and adaptations for daily living will be presented for each visit.

Fibrodysplasia Ossificans Progressiva-Physical Function Questionnaire

The FOP-PFQ consists of 28 questions in the adult version and 26 questions in the paediatric version which are scored on a scale of 1 to 5.

The total score will be calculated as follows:

- Adult version: the sum of the scores from each question which will range from  $28 \times 1 = 28$  to  $28 \times 5 = 140$ ;
- Paediatric version: the sum of the scores from each question which will range from  $26 \times 1 = 26$  to  $26 \times 5 = 130$ .

The upper extremities subscore will be calculated as follows:

- Adult version: the sum of the scores from 15 questions (Questions 1-12, 14, 25 and 26) which will range from  $15 \times 1 = 15$  to  $15 \times 5 = 75$ ;
- Paediatric version: the sum of the scores from 18 questions (Questions 1, 2, 6-11, 16-19 and 21-26) which will range from  $18 \times 1 = 18$  to  $18 \times 5 = 90$ .

The mobility subscore will be calculated as follows:

- Adult version: the sum of the scores from 13 questions (Questions 13, 15-24, 27 and 28) which will range from  $13 \times 1 = 13$  to  $13 \times 5 = 65$ ;
- Paediatric version: the sum of the scores from 8 questions (Questions 3, 4, 5, 12-15 and 20) which will range from  $8 \times 1 = 8$  to  $8 \times 5 = 40$ .

Missing scores for individual questions will not be imputed, but they will be taken into account according to the rules described below:

- (1) If more than 20% of the questions contributing to the total score are missing, the total score will not be calculated. It will be considered as missing;
- (2) If less than 20% of the questions contributing to the total score are missing, the total score will be calculated by summing all observed question scores, divided by the number of questions that were answered and by multiplying this average score by the total number of questions that were meant to be answered (i.e. × 28 for the adult version and × 26 for the paediatric form).

The two rules described above also apply to the upper extremities subscore and the mobility subscore.

As the analysis for FOP-PFQ will be performed across all participants (paediatric and adult) and the number of contributing questions differs, the scores will be transformed to reflect a percentage of worst score. The percentage of worst score ranges from 0% to 100% with 0% indicating the best possible function and 100% indicating the worst possible function.

The % of worst scores (for total score, upper extremities subscore and mobility subscore) as well as the change from the Baseline Visit will be presented for each visit overall and by age group.

PAGE 63 OF 287

Patient-Reported Outcomes Measurement Information System Global Health Scale

For the adult version, the global physical health and global mental health scores will be calculated as follows:

- Global physical health scores will be calculated as the sum of scores from Questions 3, 6, 7 and 8 and will range from 4 (worse health) to 20 (better health);
- Global mental health scores will be calculated as the sum of scores from Questions 2, 4, 5 and 10 and will range from 4 (worse health) to 20 (better health).

In the calculation of the above scores, the Question 7, 8 and 10 will be rescaled as shown in Table 5.

If a participant is missing any of the contributing raw scores, the corresponding score (global physical health or global mental health score) will not be calculated for that participant.

Raw Score Questions **Rescaled Score** 0 1-3 4 4-6 7-9 10 1 8 and 10 5 1 4 2 3 3 4 2

 Table 5
 Rescaled Global Physical and Mental Health Scores for the Adult Version of PROMIS

PROMIS=Patient-Reported Outcomes Measurement Information System

For the paediatric version, the total score will be calculated as the sum of scores from the first 7 questions and will range from 7 (worse health) to 35 (better health).

If more than 3 questions contributing to the total score are missing, the total score will not be calculated. It will be considered as missing.

If not more than 3 questions contributing to the total score are missing, the total score will be calculated by summing all observed question scores, divided by the number of questions that were answered and by multiplying this average score by the total number of questions that were meant to be answered (i.e.  $\times$  7).

The global physical health score, the global mental health score and the total score will also be converted into T-scores. T-score distributions are standardised such that a value of 50 represents the average (mean) for the general population and increments of  $\pm 10$  points represent  $\pm 1$  standard deviation away from the norm. Higher T-scores indicate better physical/mental health. A T-score <50 indicates worse health than the general population, while a T-score >50 indicates better health.

For example, a participant who has a T-score of 60 is 1 standard deviation better (healthier) than the general population. Conversion tables are provided in Appendix 2.

Actual values as well as the change from the Baseline Visit in mean global physical and mental health score converted into T-scores (for participants ≥15 years old) and mean total score converted into T-scores (for participants <15 years) will be presented for each visit overall and by age group.

